It is estimated that 20% of patients hospitalized for COVID-19 will have persistent symptoms after 5 weeks and 10% after 12 weeks. However, in non-hospitalized patients it was found that between 32.6% and 87.4% present at least one persistent symptom after months of having suffered from COVID-19. To signs and symptoms that began during COVID-19 infection or after her, and last beyond 12 weeks from the date of onset of symptoms, and not can be explained by alternative diagnosis is called persistent COVID. The The importance of this syndrome was warned by the WHO on October 30, 2020 by its Director General due to the number of people with this condition and the effects on their health. However, it only physical symptoms are considered and the mental health of patients is not included, although addressing this appearance is an integral part of your ref health. Being multisystemic, this syndrome requires an approach multidisciplinary, capable of studying physical, cognitive, psychological and social aspects. So far, it is known that persistent COVID syndrome can have disabling consequences for prolonged periods. These sequelae can involve a wide variety of symptoms, from extreme fatigue, muscle and joint pain, shortness of breath, palpitations, loss permanent loss of taste and smell, gastrointestinal upset, and problems with attention, memory, and cognition. However, the exhaustive understanding of the syndrome, its monitoring and the search for treatments singles have not yet been determined. The Decentralized Medical Trials Manual of the Association of Research Organizations Clinic (ACRO) recommends decentralized medical testing or partially decentralized, organized around the patient. Decentralization refers to monitoring of patients from their place of residence to prevent them from going to health centers in regular way. The decentralization can be total or partial depending on whether during the treatment they never go to a health center or do so occasionally. These types of studies can be carried out through the use of telemedicine and artificial intelligence tools, the use of remotevisits and visits to the patient's home to carry out the collection of biological samples necessaryfor carry out the study. On the other hand, the design around the patient is intended to be friendly and allow the patient's perspective to be at the heart of the study, considering the patient's well-being from a comprehensive perspective (clinical and psychological). This approach allows the patient to know their perspective of physical and emotional health and feelaccompanied throughout the clinical study, which improves patient adherence to the clinical trial. There are no specific treatments yet for persistent COVID syndrome, and given the range of symptoms persistent, treatments should focus on generating a systemic improvement of thepatient, especially for improve her quality of life. Echinochroma A (EchA) is a pigment derived from sea urchins which is known for its antioxidant power and its proven benefits for human health, especially heart disease and inflammatory pathologies. Oral administration of EchA in patients with syndrome Persistent COVID can bring many benefits: reduced inflammation, elimination of ROS and the induction of glutathione (GSH) pathways, among the most prominent. Also, due to the pharmacological activities of EchA, its low level of toxicity and high bioavailability, is hypothesized which will contribute highly positive clinical benefits to patients with sequalae from COVID. Therefore, the objective of this project is to carry out a partially decentralized study around the patient with COVID-19 sequalae from a multidisciplinary perspective, with an intervention when administering a Dietary supplement based on sea urchin roe rich in Echinochrome A.

Objectives and Hypothesis

1 To perform an outpatient treatment with a Dietary supplement based on sea urchin roe rich in Echinochrome A in patients with sequalae from COVID-19.

a - H1-1: The Dietary supplement improves the clinical status of patients with COVID-19 sequelae

Justification: Treatment with the Dietary supplement rich in Echinochrome A is expected to activate the metabolism of glutathione, improves the functioning of the mitochondria, decreasing the cellular oxidation state and general inflammation of the endothelium, generating an improvement in the clinical status of patients and reducing your recovery time.

b - H1-2: The Dietary supplement based on sea urchin roe rich in Echinochrome A reduces the recovery time of patients with sequelae from COVID-19

Justification: Treatment with the Dietary supplement by activating the metabolism of glutathione and decrease cell oxidation and inflammation of the endothelium, reduces recovery time of the patient.

2 Perform a multidisciplinary follow-up of the evolution of the patient with COVID sequalae, involving clinicians, pulmonologists, neurologists, counselors, biochemists and Researchers.

a - H2-1: The multidisciplinary approach allows a deep understanding of the symptoms of the sequalae from COVID and its evolution

Justification: This approach will allow for a comprehensive analysis. Can be tracked simultaneous clinical, neurological, neurological, cardiological, psychological, biochemical approach, with a adequate analysis of the data, allowing a deeper understanding of the symptoms.

b - H2-2: The multidisciplinary approach generates high adherence to the study and allows a emotional accompaniment of patients, improving their mood Justification: the multidisciplinary approach will allow comprehensive monitoring of patients and increase knowledge about the persistent symptoms found in the patients with sequalae from COVID-19. In addition, psychological support will increase the patient's adherence to treatment and will improve your emotional state when accompanied.

3 Follow up with patients on a daily basis using a partially decentralized through the use of telemedicine in patients with the COVID sequalae.

a - H3-1: The partially decentralized approach by telemedicine allows a daily follow-up of the symptoms of patients with sequalae from COVID, thus relieving the health system

Justification: Daily telemedicine follow-up will decrease the frequency with which patients approach or communicate with doctors, relieving the daily tasks of health personnel and administrative work that normally involves a medical test, obtaining high-quality data anyway.

b - H3-2: The partially decentralized by telemedicine allows the emotional accompaniment of the patients increasing their adherence to the study and improving their mood and emotional state.

Justification: The decentralized design is focused on the well-being of the patient, providing a daily accompaniment by telemedicine and emotional weekly. In addition, patients can Communicate through the telemedicine system in case of doubts or concerns, providing greater

security. As well as they will be able to have access when requesting it of their progress to be able to understand how they evolve the consequences.

Partially decentralized design focused on the patient.

It is proposed to make a partially decentralized design around the patient following the ACRO recommendations. These studies use digital technologies to optimize resources of the health system and to allow the patient to have daily contact with the objective to accelerate the production of results and create an efficient dynamic of the research process. This type of design puts the patient at the heart of interactions and allows for more efficient bonding of all the actors involved. In this case, the patient with symptoms of persistent Covid-19 is detected in the Hospitals, the treatment is offered to the patient according to medical criteria, the patient's file is filled out with the clinical history and through informed consent, the participant is recruited in this comprehensive care model with intervention. We proceed to complete the Digital Entry Form of the patient where their data is uploaded and a photo of the informed consent document is attached signed, the group of CONICET-UNPSJB Researchers receives the information about the patient and by randomized algorithm, the delivery of the nutraceutical or the placebo is determined and sent to the patient's address along with pertinent information. The ID of each patient in the entire Health System telemedicine will be your ID. Once loaded, the link of the digital self-tests will be sent to your WhatsApp designed for this study, which the patient must complete and send daily as a health report and you can use it whenever she needs it. SKYMED is governed by Law 25,326 on Data Protection Personal and Law 26,529 of the Right of the Patient and has the due Confidentiality Agreements that protect and commit all parties in your application during the use of the platform. Starting from that moment the Muñiz Hospital Hemostasis Team and the Team of Psychological Consultants Receive patient information. From here, through the calendar of the telemedicine system SKYMED organizes shifts for each patient with Hospital Muñiz for blood collection, interviews with the psychological accompaniment and the medical follow-ups by the different doctors and hospitals involved. The patient fills out the form every day and this information can be monitored instantly. If the patient has symptoms that show deterioration, sends an alert to the medical team through the triage system that SKYMED has based on artificial intelligence. The patient has an instant messaging interface to make inquiries during the treatment in addition to the weekly interviews with the team of psychological consultants and the Monthly visits to hospitals. The evolution of the patient is carried out weekly and at the end of the study the results are already very advanced to be able to conclude on them. This approach seeks to accompany the patient throughout the medical study from a multidisciplinary, considering the practical aspect of decentralization with the emotional care that patients with persistent COVID syndrome require.

The SKYMED telemedicine system has been used successfully for a year in Chubut (Lago Puelo) and uses the key performance indicators (KPIs) established by the WHO for the care of COVID-19, in order for the doctor to evaluate the patients, and, with the help of the artificial intelligence digital technology, early detection of symptoms that are considered within a serious picture to send alerts to the health system. For this particular study, it was adapted the system with a design and interface or dashboard based on the KPIs specified by the team medical, scientific and psychological consultants, for the monitoring of the participants, the collection and data processing, and immediate accessibility to the results in the interface on a cell phone, tablet or PC of patients with COVID-19 sequalae. Since there are very few scales around the patient that adequately reflect the clinical situation of patients with sequalae from COVID-19 and that

evaluates its evolution in a comprehensive way to integrate symptom monitoring so that indepth symptom assessment is possible; It will be used a brief and easy-to-use self-report questionnaire that will consist of different scales to perform a comprehensive assessment and can be used for repeated measurements over time to monitor the progress. The scales were selected according to the recommendations of Sanz Almazán et al (2021), who analyzed which would be the most appropriate scales to assess persistent symptoms that found in the persistent COVID syndrome, as well as its limitations and possible improvements. So daily clinical data will be evaluated. The questionnaire that assesses mood will have a psychoeducational functionality in itself since it will provide self-exploration and self-management tools emotional that will be answered 2 times a week.

In SKYMED, the patient completes the entire questionnaire at the indicated frequency. The system sends reminders to take the surveys at different times of the day and/or week to ensure your compliance. In turn, doctors, psychological and biochemical consultants can upload the information that they collect per patient. The scientists of the team will carry out the analyzes on a weekly basis during the study as the data is collected by the SKYMED system. The final report will be once the study is completed.

The psychological accompaniment will be carried out through a weekly virtual Zoom meeting of 30 minutes during the three months of treatment with the psychological consultant, in which he will be given accompaniment and emotional support hoping to sustain their adherence to it (Centered Approach in the Person. Likewise, face-to-face evaluations will be carried out with specialist doctors, at the beginning of the medical test and once a month after beginning the treatment, until its completion. In these evaluations will carry out a complete clinical and psychological study. Face-to-face evaluations are also carried out with the specialists, at the beginning of the medical test and once a month after starting the treatment, until its completion. In these evaluations, a complete clinical study will be carried out, evaluating the presence of cough, chest pain, dyspnea by mMRC scale, quality of life by EuroQOL scale, spirometry will be performed (FVC, FEV1, FEV1/FVC), the walk test of 6 minutes, a HRCT of the Chest, an electrocardiogram, the evaluation of fatigue measured with the MFI scale, the cognitive evaluation will be carried out with the MMSE (minimental State) scale, ACE-R (Addenbrooke's Cognitive Examination), attention by San of Digits forward, Digits and signs (WAIS-III), Trial Making A and Stroop Test; executive function with Trial Making B, word generation (phonological verbal fluency), FAB (Frontal Assessment Battery), clock test (on command) and analogies (WAIS-III); Language will be evaluated with the Boston Nomination Test and through semantic verbal fluency; Verbal Memory will be evaluated by the RAVLT test (Rey auditory verbal learning test), Visual Memory with the Rey Figure (evocation and recognition), Visuospatial ability with the Rey Figure (copy) and the clock test (Copy) and Mood assessment with the Beck Inventory. Finally, blood samples will be taken from the patients to perform a complete blood count, platelets, white blood cells and formula in absolute and relative values, C-Reactive Protein, Ferritin, D-Dimer and Von Willebrand Factor.

SKYMED telemedicine

The telemedicine System and Remote Patient Control SKYMED complies with the quality standards established in the Design Quality Manual for ACRO Decentralized Clinical Trials (Association of Clinical Research Organizations for its acronym in English), regarding the possibility of entering data by the patient and the equipment intervening remotely, as well as

that the system is subject to the laws and regulations of data protection and privacy that regulate these types of data released. It also meets the Total Quality Control standards, having been tested with constant improvement in use for 13 months for COVID-19 control, providing connectivity and solid infrastructure because it ensures the integrity and security of electronic records, accuracy and precision of measurements, technological solutions are fit for purpose. In addition, a user manual is provided where the flow and collection of data is described, it has backup backup of the entire system, storage, filing and availability for retrieval of source documents and information electronics during and after the test. On the other hand, there is a management plan in case of failure for all the parties, they are trained to use the system and adequate support is provided to all parties, articulating the investigators in a clear manner the procedures for decentralized clinical trials, it is added efficiency, cost savings by reducing waste and contributes to reducing climate change. The risk is minimized because: users are restricted with the use of unique and non-transferable credentials for entry into the system; there is no resistance to change because users and participants are willing to the use already proven in effectiveness of SKYMED, interfaces of known use and easy access are used, and alternative plans exist if a participant is unable to access for any reason; assistance is provided permanent technique to ensure effectiveness in the design of the system infrastructure; the system has optimal technological interoperability and data integration; constant training is given to new processes to all users; the best security standard is provided with the best provider technological; there is an optimal governance structure; It has a large data loading space that prevents system overload; SKYMED lowers costs and provides efficiency in studies focused on the patient minimizing the administrative work of the evaluation team and providing access to information processed and reliable for strategic decision making 24 hours a day, 7 days a week.

Ethical and environmental safeguard

This research project will not affect human rights nor will it be the cause of any eventual damage to the environment, animals and/or future generations. All work done previously carried out in compliance with the Biosafety and Environmental Safety Standards in force, so its realization will not have any impact on the environment. Biological material (blood samples human) will be processed in a biological safety cabinet and all the elements and reagents used properly discarded following the standards indicated by the Health and Safety Committee of the Hospital F. J. Muñiz. In this sense, the Hospital has a pathological waste management service. On the other hand, the methodology included in this project has been endorsed by the Ethics Committees of the hospitals.

Physicians will invite patients and/or their immediate family members to participate in the research study, explaining in a detailed and understandable way the characteristics of the study and future studies related to sequelae in COVID-19. Informed consents are approved by the Committees of Ethics and/or Teaching and Research of the Hospitals involved. In Argentina there is a law that protects personal information (Law No. 25,326 on Data Protection Personal) that establishes the integral safeguard of data settled in files or records, be they public or private, to guarantee the right to honor and privacy of people. When is made reference to "Client's personal data" is about the personal data of which the Institutions authorized are controllers and that OcusCloud processes in the course of providing the SaaS (Software as a service) SkyMeD. The terms "controller", "processor", "process", "processed", processing" and "personaldata" used, are defined according to the Union Directive 95/46/EC European Union, except as defined by the corresponding data protection legislation. OcusCloud guarantees under the

clauses of a confidentiality agreement, in all media / systems that are under its control and guardianship, the implementation of the technical and organizational measures that are necessary to protect the data provided. There is also Law 26,529 of the Right of the Patient, in force since February 2010, which regulates the civil relations between the patient with the doctors and with the institutions of Health and legislates on the information that the doctor must give and that the patient must receive regarding clinical documentation. The information and clinical documentation of the patient has the due protection of its privacy and the confidentiality of its sensitive data. This includes the statistical secrecy, in relation to the development of databases in the health system, by which the statements and/or individual information may not be communicated to third parties or used, disseminated or published in such a way as to allow the person or entities to be identified. sensitive data related to the patient are protected by confidentiality and privacy as well as by the data from the investigation. Only researchers will have access to this information directly related to the trial and the members of the Teaching and Research Committees and/or Hospital Ethics. All adverse effects will be reported to the Ethics Committees instantly according to current national laws, whether or not associated with the administered product. The researchers participating in this project know and carry out the safeguards provided for in all ethical, legal and legal requirements, established in the National bioethical standards -ANMAT provision 5330/97- and International -NurembergCode, declaration of Helsinski version 2008 and its modifications, universal declaration on the human genome and human rights approved by the General Conference of UNESCO 2005 and according to the regulations of the International Declaration on the human genetic data UNESCO2003, the Universal Declaration on Bioethics and guidance for Human Health Research (GISH), resolution 1480/2011 MSN. The counselors involved they know and follow the rules of the Professional Code of Ethics of the Argentine Association of Counseling.

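### H2-2, H3-1 and H3-2 claim effects of the care model, but both arms receive that model, so only their feasibility parts can be answered

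*Protocol*

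**What the plan says.** Protocol, Objectives and Hypothesis, lists six hypotheses. Two concern the supplement (H1-1, H1-2) and four concern the way care is delivered (H2-1, H2-2, H3-1, H3-2). Three of those four contain a claim of effect:

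- **H2-2:** "H2-2: The multidisciplinary approach generates high adherence to the study and allows a emotional accompaniment of patients, improving their mood". Its justification expects psychological support to raise "adherence to treatment and will improve your emotional state when accompanied".
- **H3-1:** the telemedicine approach "allows a daily follow-up of the symptoms of patients with sequalae from COVID, thus relieving the health system". Its justification states: "Daily telemedicine follow-up will decrease the frequency with which patients approach or communicate with doctors".
- **H3-2:** telemedicine allows emotional support of patients, "increasing their adherence to the study and improving their mood and emotional state". Its justification names "daily accompaniment by telemedicine and emotional weekly" as part of the mechanism.

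The section on the partially decentralized design gives the order of events. After consent, "the participant is recruited in this comprehensive care model with intervention". Then, "by randomized algorithm, the delivery of the nutraceutical or the placebo is determined and sent" to the patient's home. The daily self-report forms, messaging, weekly half-hour psychological sessions over three months, and face-to-face evaluations at the start and monthly are all described for patients in general, with no distinction by arm.

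**The concern.** To say that something increases adherence, improves mood or reduces contacts with doctors is to compare with what would have happened without it. The protocol describes no such comparison for the care model: no usual-care arm, no run-in period without the model, no historical or external reference.

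Two kinds of unsupported conclusion could follow:

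- **Mood.** A change from baseline would mix the care model with natural recovery, regression to the mean, placebo response and, in one arm, any supplement effect. An improvement could not be credited to the model.
- **Adherence and doctor contacts.** There is no reference value, so an observed level cannot show a rise or a fall. The protocol also lists no outcome for doctor contacts or staff workload, and it gives no threshold for high adherence.

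As the hypotheses are worded, good form completion or falling depression scores could be reported as evidence that the model works.

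**Working it through.** The protocol states no figure on this point, so there is nothing to reproduce. The question is one of identifiability: does exposure to the care model differ between any groups that the trial observes?

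**1. Planned exposure by arm.** The inputs come from the design section: a daily form, a weekly 30-minute session for three months, and face-to-face evaluations at the start and monthly. I assume that three months is 13 weeks and that the evaluations are baseline plus three monthly visits.

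| Component | Calculation | Supplement arm | Placebo arm | Difference |
|---|---|---|---|---|
| Daily forms | 13 × 7 | 91 | 91 | 0 |
| Weekly sessions | 13 × 1 | 13 | 13 | 0 |
| Session time | 13 × 30 min = 390 min | 6.5 h | 6.5 h | 0 |
| Face-to-face evaluations | 1 + 3 | 4 | 4 | 0 |

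The counts are illustrative. The zero differences do not depend on the assumptions.

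**2. What can be estimated.** Code three factors as absent (0) or present (1): supplement, multidisciplinary model, telemedicine. A main-effects model has 4 parameters: an intercept and three effects. The arms supply these rows, in the order intercept, supplement, multidisciplinary, telemedicine:

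- placebo arm: (1, 0, 1, 1)
- supplement arm: (1, 1, 1, 1)

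Only 2 of the 2 × 2 × 2 = 8 possible combinations are observed, and the design has rank 2 for 4 parameters. Subtracting the rows gives (0, 1, 0, 0), so the supplement effect is estimable. The only other estimable quantity is the sum intercept + multidisciplinary + telemedicine, from which neither model effect can be extracted. More participants repeat the same two rows and leave the rank unchanged.

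**3. Separating the two components.** H2-2 credits the multidisciplinary approach, and H3-2 credits telemedicine, with the same outcomes: adherence and mood. Both justifications rely on emotional support, and the design section describes a single weekly online session meant to provide it and sustain adherence. Every participant is offered all components together, so no contrast tells them apart.

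**4. What remains answerable.** The trial can describe whether daily follow-up is achieved, whether the support sessions are delivered, what adherence is reached, and how mood develops over time.

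**The case against.** The strongest defence is that objectives 2 and 3 are process aims: to carry out multidisciplinary follow-up and to follow patients daily. Much of the hypothesis wording concerns capability, the most explicit causal language sits in the justification paragraphs, and no test or success criterion is attached. The statistical analysis plan, which is not available here, may treat these hypotheses descriptively. H3-1 can also be read as a rationale for decentralised conduct compared with conventional trials, not as an effect to be estimated in this sample. On that view the point is one of minor wording.

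Part of this stands. The feasibility content is real and should be kept, and the supplement comparison is unharmed. But the claims of increased adherence, improved mood and health-system relief stand inside the numbered hypotheses, not only in their justifications. An analysis plan can decline to test them, but it cannot create a contrast in care-model exposure from the two arms described.

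Three further objections are fair but do not change the conclusion:

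- No sentence says outright that both arms receive the whole model. It is inferred from recruitment into the model before allocation and from services described for each patient. Nothing contradicts it.
- H3-2 also relies on telemedicine elements other than the weekly session, such as messaging, and the twice-weekly mood questionnaire in the telemedicine system is intended to have a psychoeducational function. These too are given to all. The questionnaire is part of the intervention as well as a measure of mood.
- Actual attendance will vary between participants. Relating attendance to outcome would be an observational analysis, not a randomised comparison.

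**Conclusion.** The concern holds. The causal parts of three of the six hypotheses (H2-2, H3-1, H3-2) have no comparator. The between-arm difference in planned exposure to the care model is 0, and the effects of its two components are merged with the intercept whatever the sample size. This rests on reading the design section as giving the whole model to both arms, which is the only reading the text supports. It does not rest on the 13-week assumption. The feasibility parts of these hypotheses, and H1-1 and H1-2, are unaffected. This should be fixed because it determines what the trial may conclude about the care model, although it does not endanger the supplement comparison.

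**What to change.** Restate only the causal parts.

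1. **H2-2 and H3-2.** Replace them with one joint descriptive feasibility objective for the combined model. Report adherence to the study as forms completed out of forms due, evaluations attended out of those due, and weekly sessions attended out of those due. Compute 95% confidence intervals across participants, because the roughly 91 forms of one person are not independent. Report the course of mood descriptively, using the Beck Inventory already collected at the face-to-face evaluations. Reword the justifications to match, including the H2-2 statement about adherence to treatment.
2. **H3-1.** Keep the feasibility claim that telemedicine permits daily follow-up. Delete the health-system-relief claim and the fewer-contacts claim in the justification, or limit them to a description of contacts that the telemedicine system already records.
3. **Add a sentence** such as: No effect of the multidisciplinary or telemedicine model will be inferred from this trial; causal inference is reserved for the comparison of supplement with placebo.

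The cost is the rewording of three hypotheses and their justifications. The claim about the care model becomes descriptive, and the claim of relief to the health system is lost. No patients, visits or measures are added: the forms, evaluations, sessions and Beck Inventory are already in the protocol, and contacts are described only if they are already recorded.

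### Does the protocol's allocation workflow leave the scientists who analyse the data weekly unblinded to treatment?

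*Protocol*

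**What the plan says.** All the relevant workflow text is in the protocol section *Partially decentralized design focused on the patient*.

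- **Entry and allocation.** The hospital recruits and obtains consent, and the digital entry form is completed; "a photo of the informed consent document is attached signed". Then the research group of "Researchers receives the information about the patient and by randomized algorithm, the delivery of the nutraceutical or the placebo is determined and sent". Delivery is by dispatch to the home.
- **Identifier.** "The ID of each patient in the entire Health System telemedicine will be your ID", so the entry record and later outcomes share one identifier.
- **Ongoing analysis.** The "scientists of the team will carry out the analyzes on a weekly basis during the study", as SKYMED collects the data. The final report follows once the study is complete.
- **Expected use.** A sentence about each patient's weekly evolution adds that "at the end of the study the results are already very advanced to be able to conclude on them".

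Two access rules appear elsewhere. Under *SKYMED telemedicine*, "users are restricted with the use of unique and non-transferable credentials for entry into the system". Under *Ethical and environmental safeguard*, "Only researchers will have access to this information directly related to the trial", together with members of the hospital committees.

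The text at hand says nothing about masking, coded packs, a holder of the allocation list, or separation of allocation from outcome data.

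**The concern.** Only one body is named at the allocation step, and it receives a fully identified record. The objectives list researchers among the project's roles. The SKYMED description has doctors and consultants upload data while scientists analyse it. It is therefore natural to suppose that the researchers at the allocation step are the scientists who run the weekly analyses.

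If those people knew the arm, the harm could be real. Knowledge of allocation can influence which entries are queried, how missing or ambiguous values are treated, and which measures and time points are reported. That route runs through data handling, so it would reach laboratory and spirometry results as well as self-reports. The expectation that results will be far advanced by study end suggests that the ongoing analyses are meant to inform the conclusions. The two stated access rules do not separate allocators from analysts.

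**Working it through.** The protocol gives no figure on this point to reproduce. The question is what the text commits the trial to. For the worry to be a defect, three links must hold.

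**Link 1: the research group knows the arm.** In the allocation sentence, the group is the subject of the receiving verb only. The assignment is made by a randomized algorithm, and the determining and sending are in the passive with no agent. The group may operate the algorithm and post the product. Equally, the algorithm may return a pack code and another party may do the posting. The wording fits both. *Possible, not stated.*

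**Link 2: the group and the weekly analysts are the same people.** The analysts are called scientists of the team and the recipients are called researchers. The role lists make overlap plausible, but no sentence equates them. Even within one institution, the person holding a list need not be the person analysing. *Plausible, not stated.*

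**Link 3: the weekly analyses are made with the arm known.** No sentence says they compare arms. The sentence containing "at the end of the study the results are already very advanced to be able to conclude on them" is about how the individual patient evolves week by week, which can be read as patient-level follow-up. Nor does any sentence say that SKYMED stores the arm. *Not stated.*

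The supporting passages do not close these gaps:

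- A single patient identifier links entry and outcome data in most trials. It discloses treatment only if treatment is recorded under it.
- The login rule concerns entry to the platform, and the confidentiality rule concerns sensitive patient data. Neither is about allocation, so their failure to separate roles is weak evidence either way.
- Consent and recruitment precede the allocation step, so the stated order does not give recruiters foreknowledge.
- The use of a placebo shows that blinding of patients, at least, was intended.

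**Can the exposure be sized?** Two counts are available.

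- Weekly analyses: the support meetings last "30 minutes during the three months of treatment with the psychological consultant", so treatment is three months, and 3 × 52/12 = 13 weeks per patient.
- Measures named for the face-to-face evaluations: 4 symptoms and scales + 3 spirometry + 3 walk test, HRCT and ECG + 1 fatigue + 2 general cognition + 4 attention + 5 executive function + 2 language + 1 verbal memory + 1 visual memory + 2 visuospatial + 1 mood + 7 blood = 36.

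These counts should not be read together as 13 looks at 36 measures. The face-to-face measures are taken at the start and monthly, so 1 + 3 = 4 occasions. Several are components of one procedure: spirometry contributes three, and the clock test appears under two headings. Neither count says anything about whether anyone knows the arm, so neither measures bias.

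**The case for a change.** The strongest case for acting is that allocation, dispatch and custody of the key are operational matters. The protocol itself sets them out, so an SAP would not normally supply them. The research group is the only party named, and no pharmacy or independent dispatcher appears. A masking label on the front page, if there is one, would not by itself create a barrier. The remedy looks cheap: send product under a kit code and have someone outside the analysis hold the key. If that is already the practice, writing it down costs a sentence.

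Part of this stands. The protocol would be clearer if it said who holds the allocation key and whether those looking at accumulating data can see it, and asking the investigators is reasonable. The argument still moves from silence to a fault. It shows that unblinding is not excluded; it does not show that the described procedure leads to it. A low cost of rewording does not turn an omission into an error. The cost is also not known to be low, because the document does not identify a project member free of support, assessment, data handling and analysis duties to hold the key.

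**Conclusion.** No change to the plan follows. The protocol omits an operational detail that a team running a placebo-controlled trial would ordinarily settle: who keeps the link between pack and arm, and who may see it. Nothing stated is wrong or contradictory on this point. The text shows neither that the analysts know the arm nor that they are the people who allocate. Unblinding of patients, hospital assessors or counsellors is not shown either.

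The size of any bias cannot be estimated from the document, and the counts of 13 weeks and 36 measures do not substitute for an estimate.

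This conclusion assumes that the placebo is supplied in a form that does not reveal treatment to those handling the data, and that the key is kept from them. The text is compatible with that assumption but does not confirm it; neither the protocol's front matter nor the SAP was available to check. If the investigators reported that the weekly analysts hold the key, or that SKYMED displays the arm to them, the worry would be well founded and the conclusion would change.
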